### 3.11. Hexsel Depression Depth Scale

The Hexsel Cellulite Severity Scale (Hexsel CSS) is a photometric scale that looks at 5 key morphologic features of cellulite (2,3):

- A - number of evident depressions
- B - depth of depressions
- C - morphological appearance of skin surface alterations
- D - laxity, flaccidity or sagging of skin, and
- E - current classification scale based on medical literature

Each of these features is evaluated on a 4-point scale from a low of 0 to a high of 3. For this study, only “B - depth of depressions” will be assessed.

The investigator or qualified designee will use the Hexsel CSS (B) depth of depressions to assess the severity of EFP in each buttock or each thigh. The assessment will be made while the subject is in the standing position with relaxed gluteus muscles at the following visits:

- Screening visit
- Days 22, 43, and 71( EOS/ Early termination)

The labels and descriptions associated with each level of depth of depression of Hexsel CSS (B) are shown in Table 6 below.

**Table 6: Hexsel CSS (B) Depth of Depressions**

Rating	Description
0	No depressions
1	Superficial depressions
2	Medium depth depressions
3	Deep depressions

### 3.12. Medical and Surgical History

A medical and surgical history of the subject will be taken during the screening period. Medical history will include relevant diagnoses and/or procedures/therapies with onset/resolutions dates.

If onset date is unknown, then condition whether it occurred within 5 years or more than 5 years will be recorded on the eCRF.

### **3.13. Edematous Fibrosclerotic Panniculopathy Disease (EFP) History**

EFP disease history will be obtained from the subject during the screening period. The EFP disease history will include the following:

- Family history of cellulite (answered as yes, no, or unknown)
- Onset date of EFP symptoms
- Previous treatments used for EFP

### **3.14. Substance Use**

History of tobacco and alcohol use will be taken during the screening period and following information will be recorded:

- Type of substance (Alcohol/Tobacco)
- History of usage (Never/Currently/Former)
- Number of years the product was used (for current or former users)
- Stop date of using the product (for former users)

### **3.15. Prior/Concomitant Medications and Procedures**

Any medications (including OTC medication) taken during the study or within 90 days prior to Day 1 will be recorded.

Any diagnostic, therapeutic, or surgical procedure performed before the study or during the study, including the treatment of EFP will be recorded.

### **3.16. Prohibited Medications**

The following medications and procedures are prohibited for subjects during the study:

- Anticoagulants (warfarin, heparin, direct thrombin inhibitors, Factor X inhibitors) and antiplatelet agents (aspirin >150 mg/day and P2Y12 inhibitors, such as clopidogrel), which can cause additional bruising. However, the use of aspirin at a dose level of ≤150 mg per day will be permitted during study.
- Liposuction within the treatment areas.
- Injections (eg, mesotherapy); radiofrequency device treatments; laser treatment; or surgery (including subcision and/or powered subcision).
- Any investigational treatment for EFP/cellulite on treatment areas or any other investigational drug or treatment.
- Endermologie or similar treatments within the treatment areas.

- Massage therapy within the treatment areas during the 3-month period before injection of study drug.
- Creams (eg, Celluvera, TriLastin) within the treatment areas.

### **3.17. Adverse Events**

All Adverse Events (AE) occurring after signing the informed consent and through 28 days after last dose are to be recorded on the AE pages of the eCRF. Conditions existing prior to screening will be recorded as part of subject's medical history.

#### **3.17.1. Adverse Events (AE)**

An AE is any unfavorable or unintended change in body structure (signs), body function (symptoms), laboratory result (eg, chemistry, ECG, X-ray, etc.), or worsening of a pre-existing condition associated temporally with the use of the study medication whether or not considered related to the study medication. This would include AEs resulting from concurrent illness, reactions to concurrent medication use, or progression of disease states (excluding the disease under study). A condition present at baseline that worsens after initiation of study treatment will be captured as an AE; the onset date will be the date the event worsened.

#### **3.17.2. Serious Adverse Events (SAEs)**

Serious adverse event are those AEs that meet any of the following criteria:

- Results in death
- Life-threatening event
- Results in or prolongs an inpatient hospitalization
- Results in permanent or substantial disability
- Is a congenital anomaly or birth defect
- Any important medical event that may jeopardize the subject or may require medical intervention to prevent one of the outcomes listed above

#### **3.17.3. Adverse Events of Special Interest**

AEs such as bruising, ecchymosis, hematomas, and contusions that occur remote to the site of drug administration, or any hypersensitivity reactions, including anaphylaxis, will be recorded as an AE of special interest and reported as an AE or SAE as appropriate.

In addition, local AEs associated with the injection site, including bruising, pain, nodules/mass, ulceration, erythema, pruritus, swelling, and/or induration, will be recorded.

### **3.18. Clinical Safety Laboratory Tests**

Blood and urine samples will be collected for testing the following clinical laboratory parameters during the screening period and at EOS.

**Table 7: Clinical Safety Laboratory Parameters**

Hematology	Biochemistry	Urinalysis
Hemoglobin	Glucose	Glucose
Hematocrit	Sodium	Protein
Red blood cell	Potassium	Specific gravity
White blood cell (WBC)	Calcium	pH
Platelets	Chloride	Ketones
WBC Differential	Carbon dioxide (CO 2 )	Bilirubin
	Inorganic phosphate	Urobilinogen
	Blood urea nitrogen (BUN)	Nitrite
	Creatinine	Blood*
	Creatinine clearance	Leukocytes*
	Aspartate transaminase (AST)	
	Alanine transaminase (ALT)	
	Gamma-glutamyl transferase (GGT)	
	Total bilirubin (TBL) (direct bilirubin reflex if elevated)	
	Albumin	
	Alkaline phosphatase (ALP)	
	Uric acid	

\*Microscopic examination will be performed if blood or leukocytes are detected by dipstick.

Any clinically significant laboratory abnormality observed, will be considered as an AE or SAE as appropriate.

### 3.19. Pregnancy Test

Female subjects of child bearing potential must have negative pregnancy test at Screening and Day 1 to be enrolled in the study. Female subjects of child bearing potential will undergo a serum pregnancy at the Screening Visit and urine pregnancy tests at Days 1, 22, and 43 prior to study drug administration and at Day 71 (EOS). Additional urine pregnancy tests will be performed at the discretion of the Investigator when required.

### 3.20. Vital Signs

Vital signs measurements will be taken at Screening, Day 1, 22, 43, and at the EOS visit. On treatment visits (Days 1, 22, and 43), vital signs will be assessed at 4 hours prior to, and at 15 and 30 minutes after study drug administration.

Vital signs measurements include: systolic and diastolic blood pressure, respiratory rate, pulse rate, body temperature, height, and body weight.

Height and body weight measurements will be taken at Screening. Body weight will also be measured at Day 1 and at EOS visit.

Any abnormality in vital sign observed, will be considered as an AE or SAE as appropriate.

### 3.21. 12-Lead Electrocardiogram (ECG)

A 12-Lead ECG will be recorded during the screening period while the subject is in supine position for at least 5 minutes before the recording is conducted.

ECGs will be assessed by the Investigator and graded as:

- Normal
- Abnormal, not clinically significant
- Abnormal, clinically significant

Any abnormality in ECG observed, will be considered as an AE or SAE as appropriate.

### 3.22. Physical Examination

A complete physical examination (by body system) on each subject will be performed at screening. This evaluation will include an examination of head, eyes, ears, nose and throat, skin, neck, chest, heart, lungs, breasts, lymph nodes, abdomen, back, extremities, musculoskeletal system, and central nervous system. Physical examination findings will be recorded as normal, abnormal or not done as not standard of care.

Any abnormality in physical examination observed, will be considered as an AE or SAE as appropriate.

The subject's skin type will be assessed at screening using the Fitzpatrick scale shown below.

**Table 8: Fitzpatrick Scale**

I	Pale white skin, blue/hazel eyes, blond/red hair	Always burns, does not tan
II	Fair skin, blue eyes	Burns easily, tans poorly
III	Darker white skin	Tans after initial burn
IV	Light brown skin	Burns minimally, tans easily
V	Brown skin	Rarely burns, tans darkly easily
VI	Dark brown or black skin	Never burns, always tans darkly

### 3.23. Immunogenicity

Immunogenicity variables include anti-AUX-I/anti-AUX-II binding (ie, anti-drug) and neutralizing antibody results. Serum samples will be collected at Day 1 (before injection) and at the Day 71 (EOS) visit for the determination of serum anti-AUX-I and anti-AUX-II antibody levels and neutralizing antibodies to AUX-I and AUX-II. A subset (based on every other sample from the Day 71 upper and lower quartiles of all positive binding antibody titers) of subject samples will be tested for neutralizing antibodies from the Day 1 and Day 71 visits; additional samples will be retained.

## 4. STUDY PARAMETERS

### 4.1. Subject Disposition

Subjects will be considered as completing the study if they complete all the scheduled treatment and the Day 71/EOS visit. A premature discontinuation will occur if subjects discontinue treatment and/or participation in the study. Subjects who discontinue early for any reason, will be

encouraged to have all Day 71/EOS procedures and assessments completed at an early termination visit.

The reason for early discontinuation will be recorded in eCRF for the subjects who do not complete the study. The reason of screen failure will also be recorded in eCRF for subjects who are not enrolled and are considered screen failures.

#### **4.2. Protocol Deviations**

Protocol deviations will be identified and documented prior to database lock. Protocol deviations will be derived from the eCRF data and will be obtained from the clinical monitoring reports. All deviations from these two sources will be reconciled and duplicate deviations will be removed. When a deviation is both found in the database and in clinical monitoring reports, in most cases the text of the deviation from the database will be retained. The exception to this rule will occur if the deviation from the monitoring report provides important information not found in the database. In that case, the information will be reconciled in the database.

Possible protocol deviations include, but are not restricted to the following deviation types:

- Ineligible subject/study entry criteria not satisfied
- Informed consent not completed correctly
- Non-compliance of study treatment
- Prohibited medications/procedure
- Visit/procedure missing or out of window

The Endo study team will approve all final protocol deviation assignments and classify them as either major or minor during a protocol deviation review meeting held prior to the database lock.

#### **4.3. Prior Concomitant and Follow-up Medications**

All medications will be coded using World Health Organization (WHO) Drug Dictionary - Global B3 format 2018, by active ingredient and WHO anatomical therapeutic chemical (ATC) classification of ingredients.

A prior medication is defined as any medication taken prior to the first injection of the study drug.

A concomitant medication is any medication taken between the date of first injection of the study drug and the date of last injection of study drug or the medication is reported as ongoing. Any medications started after the last injection of the study drug will be considered as follow-up medications.

#### **4.4. Prior EFP Treatment**

Prior EFP treatment will be obtained from the prior/concomitant medication and/or prior/concomitant procedure pages of the eCRF. If on either of these pages a medication or procedure is reported with the indication 'EFP/cellulite' with a start date prior to the first injection of study drug, then the medication or procedure will be considered a prior EFP treatment.

All medications will be classified as EFP Drug. All procedures will be classified into one of the following groups:

- Liposuction
- Laser
- Massage
- Radiofrequency
- Mesotherapy
- Cream
- Other

The classification will be reviewed and approved by the study medical monitor. Any EFP treatment used after the Day 1 visit will be noted and reported as a protocol violation.

#### **4.5. Efficacy Parameters**

##### **4.5.1. Improvement in Aesthetic Appearance using 3-D Photographic Image**

Improvement from baseline in aesthetic appearance of the treatment area will be assessed by a blinded central assessor using a 5-point Likert Scale in each treatment area (ie, from worse to very much improved, for aesthetic improvement) at Day 22, 43 and 71. The efficacy will be evaluated at Day 22, 43 and 71.

##### **4.5.2. Change in Dimple Analysis Parameters using 3-D Photographic Image**

Dimple analysis parameters, max length, max width, surface area and volume between the dimple base and interpolated surface, will be assessed by IAT in each treatment area at Day 1, Day 22, 43, and 71/ET. The change in these parameters from Day 1 will be evaluated at Day 22, 43, and 71/ET.

##### **4.5.3. Change from Baseline in Dimple Depth Depression by Hexsel CSS (B)**

Dimple depth depression will be assessed by Investigator at the Screening visit, Day 22, 43, and 71 using Hexsel CSS (B) depth of depressions scale and graded as; No depressions (0), Superficial depressions (1), Medium depth depressions (2) and Deep depressions (3).

The change from baseline at each post baseline visits will be analyzed and summarized for Hexsel CSS (B) depth of depressions scale score of each treatment area.

#### **4.6. Safety Parameters**

##### **4.6.1. Adverse Events**

Adverse Event verbatim terms as reported by the investigator of adverse event will be mapped to System Organ Class (SOC) and Preferred Term (PT) using the Medical Dictionary for Regulatory Activities (MedDRA) dictionary. The version to be used will be defined in Data Management Plan (DMP).

#### **4.6.1.1. Treatment Emergent Adverse Events (TEAEs)**

TEAEs are defined as any AEs that occur or worsen (increase in severity) on the same day or after the first injection on Day 1.

The following rules will apply in cases where the start date of an AE is known:

- If the AE onset date is prior to first injection on Day 1, then the AE will not be considered a TEAE.
- If the AE onset date or date of AE worsening is equal to or later than first injection on Day 1, then the AE will be considered a TEAE.

Refer to section 6.4.1.1 to identify TEAE status when start date of an AE is unknown.

#### **4.6.1.2. Intensity of Adverse Events**

Intensity (or severity) of AEs will be graded as “Mild”, “Moderate” or “Severe”. For AEs with missing severity, the most severe assessment will be imputed for analyses, following worst case principle.

#### **4.6.1.3. Relationship to Study Drug**

Causal relationship of AE with study drug will be classified by the Investigator and will be reported as follows:

- Not related
- Unlikely related
- Possibly related
- Probably related

Related adverse events are AEs with the relationship described by the investigator as “probably related” or “possibly related”. “Not related” or “Unlikely related” causality assessments are considered as negative causality.

Any missing relationship of an AE to study drug will be considered as related to study drug for the analyses, following worst case principle.

#### **4.6.2. Vital Signs and Clinical Laboratories**

##### **4.6.2.1. Potentially Clinically Important Laboratory Values**

Potentially Clinically Important (PCI) laboratory values are presented in [Table 9](#) below.

**Table 9: Potentially Clinically Important Laboratory Criteria**

Parameter	PCI Low: Less than or equal to	PCI High: Greater than or equal to
Hemoglobin (g/L)	100	190
Hematocrit (%)	30	60
Platelets (10  /L)	100	650
ALT (U/L)		3×ULN
AST (U/L)		3×ULN
Creatinine (µmol/L)		300
BUN (mmol/L)		12

ALT=Alanine transaminase; AST=Aspartate transaminase; BUN=Blood urea nitrogen; ULN=Upper limit of normal

**4.6.2.2. Potentially Clinically Important Vital Sign Values**

Vital sign values are PCI if they meet both the observed value criteria and the change from baseline criteria. The PCI vital sign values are presented in Table 10 below.

**Table 10: Potentially Clinically Important Vital Sign Criteria**

Parameter	PCI Low	PCI High
Systolic Blood Pressure	≤90 mmHg and decrease ≥20 mmHg from baseline	≥180 mmHg and increase ≥20 mmHg from baseline
Diastolic Blood Pressure	≤50 mmHg and decrease ≥15 mmHg from baseline	≥105 mmHg and increase ≥15 mmHg from baseline
Pulse Rate	≤50 bpm and decrease ≥15 bpm from baseline	≥120 bpm and increase ≥15 bpm from baseline
Respiratory Rate	≤8 brpm and decrease ≥7 brpm from baseline	≥25 brpm and increase ≥7 brpm from baseline
Temperature		≥38.3°C and increase ≥1.1°C from baseline

bpm=Beats per minute; brpm=Breaths per minute

**4.6.3. Bruise Analysis using L\*A\*B\* Coordinates**

Bruised tissue and normal tissue will be assessed using two L\*A\*B\* color measurements at Day 1, 4, 8, and 15. The change in visual perception between two colors, ie, ΔE will be computed as follows:

**Bruised Tissue vs. Normal Tissue at Day 1, 4, 8, and 15**

$$\Delta E \text{ (Bruised vs. Normal)} = [(L^*_B - L^*_N)^2 + (A^*_B - A^*_N)^2 + (B^*_B - B^*_N)^2]^{1/2}$$

Where, ΔE = Color difference between Bruised Tissue vs. Normal Tissue)

- L\*B = Bruised Tissue L\*
- L\*N = Normal Tissue L\*
- A\*B = Bruised Tissue A\*
- A\*N = Normal Tissue A\*
- B\*B = Bruised Tissue B\*
- B\*N = Normal Tissue B\*

**Normal Tissue of Follow-up Visits vs. Normal Tissue of Day 1**

$$\Delta E (\text{Normal} - \text{Day 1 vs. Follow-up}) = [(L^*_F - L^*_{D1})^2 + (A^*_F - A^*_{D1})^2 + (B^*_F - B^*_{D1})^2]^{1/2}$$

Where,  $\Delta E$  = Color difference between Normal Tissue at Follow-up visits vs. Normal Tissue at Day 1

$L^*_F$  = Normal Tissue  $L^*$  at Follow-up visit

$L^*_{D1}$  = Normal Tissue  $L^*$  at Day 1

$A^*_F$  = Normal Tissue  $A^*$  at Follow-up visit

$A^*_{D1}$  = Normal Tissue  $A^*$  at Day 1

$B^*_F$  = Normal Tissue  $B^*$  at Follow-up visit

$B^*_{D1}$  = Normal Tissue  $B^*$  at Day 1

**4.7. Other Safety Parameters**

**4.7.1. Immunogenicity**

Seropositivity and titer levels for both anti-AUX-I and anti-AUX-II antibodies will be obtained from each analyzed sample. Samples with a positive titer value will undergo a log transformation for analyses. Samples with titer level less than 1 will be assigned or imputed as a log transformed titer of zero (0) for analyses.

All samples with seropositive antibodies will be tested for neutralizing antibodies on Day 1 and Day 71. Samples will be classified as positive or negative for neutralizing antibodies based on the results of these analyses.

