14.8. Anti-AUX-I and Anti-AUX-II Antibodies

Serum samples will be collected before injection on Day 1 and at the Day 71 visit and will be tested for binding anti-AUX-I and anti-AUX-II antibody and anti-AUX-I and anti-AUX-II neutralizing antibodies.

The serum samples obtained will be processed, stored and then shipped on dry ice to the designated central clinical laboratory according to the instructions in the laboratory manual.

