17.6.8. Anti-AUX-I and Anti-AUX-II Antibodies

Anti-AUX-I and anti-AUX-II antibody levels and a subset of subject Anti-AUX-I and anti-AUX-II neutralizing antibodies will be summarized using appropriate descriptive statistics.

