## 7.9. Other Safety Parameters

### 7.9.1. Immunogenicity

The immunogenicity analysis of binding and neutralizing anti-AUX-I and anti-AUX-II antibodies will summarize the number of subjects with an immunogenicity sample, the percentages of subjects with a positive sample, and the average titer level of the positive samples at Day 1 and EOS along with summary statistics if antibody assays are conducted. The titer levels will be logarithmically transformed prior to being summarized.

The number and percentage of assayed serum samples that will detect the presence or absence of neutralizing antibodies (positive/negative) to AUX-I and AUX-II will be summarized by antidrug antibody quartiles using frequency count and percentage at Day 1 and EOS.

A listing of immunogenicity results by subject will be provided.

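### The SAP gives two incompatible rules for which samples are tested for neutralizing antibodies, and under one of them the planned neutralizing-positive percentage draws on the extreme titer quartiles only

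*SAP*

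**What the plan says.** Five places bear on neutralizing antibody testing.

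- **SAP 3.23** limits testing to "A subset (based on every other sample from the Day 71 upper and lower quartiles of all positive binding antibody titers) of subject samples", which "will be tested for neutralizing antibodies from the Day 1 and Day 71 visits; additional samples will be retained".
- **SAP 4.7.1** says "All samples with seropositive antibodies will be tested for neutralizing antibodies on Day 1 and Day 71". It mentions no subset and does not refer back to 3.23.
- **SAP 7.9.1** plans two displays. Its first paragraph covers binding and neutralizing antibodies together and includes the percentage of subjects with a positive sample. Its second says that neutralizing status (positive or negative) "will be summarized by antidrug antibody quartiles using frequency count and percentage at Day 1 and EOS". It does not say which testing rule supplies the data.
- **Protocol 14.8** says the Day 1 and Day 71 serum samples "will be tested for binding anti-AUX-I and anti-AUX-II antibody and anti-AUX-I and anti-AUX-II neutralizing antibodies", with no subset.
- **Protocol 17.6.8** speaks of "a subset of subject Anti-AUX-I and anti-AUX-II neutralizing antibodies", with no selection rule.

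The SAP's table of changes from the protocol (Table 13) covers only the mixed model. Its revision history (Table 14) describes version 2.0 as an image-analysis update. Neither mentions neutralizing antibodies.

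**The concern.** A laboratory working from 3.23 and a programmer working from 4.7.1 would each be following the SAP, yet would expect different datasets. The choice also changes what the result means. Testing every seropositive sample gives a neutralizing-positive percentage that describes seropositive subjects. Testing only the two ends of the titer distribution gives a percentage for a deliberately unrepresentative set. A reader of the report could not tell which was meant from the SAP, and 7.9.1 attaches no caveat to the overall percentage. Immunogenicity is an exploratory objective, so what is at stake is a clear descriptive result, not a test or an error rate.

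**Working it through.** The documents state no number of neutralizing antibody assays, so there is no figure to reproduce. The check is a count under each rule.

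**Inputs**
- Planned enrolment: about 60 (SAP 3.1).
- Seropositivity after three treatments: above 90% in earlier studies (protocol 8.1.2). That figure is for AUX-I and/or AUX-II; applying 90% to each antibody singly is an assumption.
- Day 1 seropositivity: not given. Prior collagenase treatment is an exclusion, so 0% to 10% is assumed.

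**Day 71, one antibody**
- Fraction of positives tested under 3.23: 2/4 quartiles × 1/2 = 1/4. Under 4.7.1: 1. Nominal ratio: 4.
- Positives: 0.90 × 60 = 54, in quartiles of 14, 14, 13 and 13.
- Under 3.23 the lower and upper quartiles hold 14 + 13 = 27. Every other sample gives 7 + 6 = 13 or 7 + 7 = 14, depending on rounding. The two middle quartiles contribute 0.
- Under 4.7.1: 54 tested, 13 or 14 in each quartile.
- Ratio: 54/14 = 3.86 to 54/13 = 4.15. Over 50 to 60 subjects and 90% to 100% seropositivity it runs from 3.7 to 4.3.

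**Day 1**

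The rules differ in kind here. SAP 3.23 tests the Day 1 samples of the selected subjects whatever their Day 1 serostatus; 4.7.1 tests only those that are seropositive. With 60 subjects that is 13 to 14 samples against 0 to 6.

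**Both days together**
- No Day 1 positives: 54/(2 × 14) = 1.93 to 54/(2 × 13) = 2.08.
- Six Day 1 positives: 60/28 = 2.14 to 60/26 = 2.31.
- Over the wider ranges above: about 1.9 to 2.4.

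**AUX-I and AUX-II selections pooled**

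If the subset is drawn separately for each antibody and a subject counts once when selected for either, more subjects are tested under 3.23. Simulation with 54 subjects positive for both gave:

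| Correlation of the two titers | Mean subjects selected | 54 / selected |
|---|---|---|
| 0 | 24.3 | 2.2 |
| 0.5 | 23.9 | 2.3 |
| 0.9 | 22.1 | 2.4 |
| 1.0 | 14.0 | 3.9 |

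**What the 3.23 percentage measures**

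Let p1 to p4 be the neutralizing-positive rates in equal-sized titer quartiles, lowest to highest. The subset targets (p1 + p4)/2, and the rate among all positives is (p1 + p2 + p3 + p4)/4. The difference is (p1 + p4 − p2 − p3)/4. The documents give no quartile rates, so the following are assumed purely to show the range:

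| Assumed rates, p1 to p4 | All positives | Extreme quartiles | Difference |
|---|---|---|---|
| 10, 20, 30, 90% | 37.5% | 50% | +12.5 points |
| 10, 35, 65, 90% | 50% | 50% | 0 |
| 10, 60, 80, 90% | 60% | 50% | −10 points |

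The sign depends on the middle quartiles, which are the ones the subset leaves out. Percentages within the upper and lower quartiles are not affected.

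**The case against.** The strongest reply is that this is one stray sentence. SAP 3.23, SAP 7.9.1 and protocol 17.6.8 can all be read as a deliberate subset design contrasting low and high titers, with 4.7.1 as the outlier. That is plausible, but nothing in 4.7.1 confines it to the subset, and protocol 14.8 has no subset either. Even if the subset was intended, the overall percentage in 7.9.1 still lacks a caveat.

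A second reply is that the denominator is known: 7.9.1 bases the quartile percentages on assayed samples, and SAP 6.1 uses non-missing values. That stands for the quartile display, but it does not say which samples are assayed.

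A third is that the matter is small. The objective is exploratory, the summaries are descriptive, no sample size depends on them, and 7.9.1 itself is conditional on the assays being run. This stands, and it limits the importance of the point.

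A reader might also infer more than the documents support:

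- *Half the quartile table will be empty.* That assumes four rows. SAP 7.9.1 does not give the number, and the table layouts are in SAP Module 2, which is not among the documents. A table with only the upper and lower quartiles would fit 3.23.
- *One rule tests four times the stated sample.* No sample is stated, and the factor of about four holds only at Day 71 for one antibody.
- *The subset percentage is biased by a known amount, or has a known loss of precision.* The quartile rates are not given, and no confidence interval is planned for this output.
- *The protocol contains the same two rules as the SAP.* It does not: 14.8 read literally covers every collected sample, seropositive or not, and 17.6.8 gives no selection rule.

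**Conclusion.** The point holds as a real, unresolved contradiction in the current SAP, with a related disagreement in the protocol. The rules differ about fourfold in subjects tested at Day 71 for a given antibody, on the assumption of 60 subjects and 90% seropositivity for that antibody. They differ about twofold when both days' samples are counted, with the assumed Day 1 range. They also disagree on which Day 1 samples qualify.

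Under 3.23 there are no Day 71 neutralizing data from the two middle quartiles. The overall percentage in 7.9.1 then does not in general estimate the rate among seropositive subjects, and a quartile table, if laid out with four rows, would have two empty at Day 71. No efficacy or main safety conclusion is touched. It should be corrected because the wording change is simple and the displays cannot otherwise be interpreted.

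**What to change.** State one testing rule, in the same words, in SAP 3.23 and 4.7.1, covering both Day 1 and Day 71 and saying whether a Day 1 sample must itself be seropositive. Say whether the quartiles are formed separately for AUX-I and AUX-II, and whether Day 71 titers define them for both the Day 1 and the end-of-study displays. Reconcile protocol 14.8 with 17.6.8. Then match 7.9.1 to the rule:

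- **If all seropositive samples are tested:** keep the overall percentage and all four quartiles.
- **If the extreme-quartile subset is kept:** show only the upper and lower quartile rows, and either drop the overall neutralizing-positive percentage or label it as not representative of all seropositive subjects.

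Keeping the subset costs wording only. Testing all positives means about 40 more subjects per antibody at Day 71 (54 − 14 = 40, or 54 − 13 = 41); the retained samples permit this. Net of the Day 1 assays that 4.7.1 would not require, the increase is 54 − 28 = 26 to 60 − 26 = 34 samples per antibody, under the assumptions above. SAP version 2.0 is dated February 2019, after the estimated last-subject completion in January 2019. Some assays may therefore already have been run, and the sponsor should check which rule the laboratory followed before settling the text.
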